12.4.8 Response Review

All responses will be reviewed by an expert independent of the study at the study's completion. Simultaneous review of the patients' files and radiological images is

the best approach.

13.0 DATA AND SAFETY MONITORING

In compliance with the Washington University Institutional Data and Safety Monitoring Plan, an independent Data and Safety Monitoring Committee (DSMC) will be specifically convened for this trial to review toxicity data at least every 6 months following the activation of the first secondary site. A DSMC will consist of no fewer than 3 members including 2 clinical investigators and a biostatistician. Like investigators, DSMC members are subject to the Washington University School of Medicine policies regarding standards of conduct. Individuals invited to serve on the DSMC will disclose any potential conflicts of interest to the trial principal investigator and/or appropriate university officials, in accordance with institution policies. Potential conflicts that develop during a trial or a member's tenure on a DSMC must also be disclosed.

The DSM report will be prepared by the study statistician with assistance from the study team, will be reviewed by the DSMC, and will be submitted to the Quality Assurance and Safety Monitoring Committee (QASMC).

Note that during the phase I dose escalation, the Principal Investigator will review all patient data at least monthly (or before each dose-escalation if occurring sooner than monthly), and provide a semi-annual report to the QASMC. The report provided to QASMC will include:

- HRPO protocol number, protocol title, Principal Investigator name, data coordinator name, regulatory coordinator name, and statistician
- Date of initial HRPO approval, date of most recent consent HRPO approval/revision, date of HRPO expiration, date of most recent QA audit, study status, and phase of study
- History of study including summary of substantive amendments; summary of accrual suspensions including start/stop dates and reason; and summary of protocol exceptions, error, or breach of confidentiality including start/stop dates and reason
- Study-wide target accrual and study-wide actual accrual including numbers from participating sites
- Protocol activation date at each participating site
- Average rate of accrual observed in year 1, year 2, and subsequent years at each participating site
- Expected accrual end date, accrual by cohort, and accrual by site
- Objectives of protocol with supporting data and list the number of participants who have met each objective
- Measures of efficacy
- Early stopping rules with supporting data and list the number of participants who have met the early stopping rules
- Summary of toxicities at all participating sites separated by cohorts with the number of dose-limiting toxicities indicated
- Abstract submissions/publications
- Summary of any recent literature that may affect the safety or ethics of the study

Further DSMC responsibilities are described in the DSMC charter.

Until such a time as the first secondary site activates this protocol, a semi-annual DSM report to be prepared by the study team will be submitted to the QASMC beginning 6 months after study activation at Washington University.

The study principal investigator and coordinator will monitor for serious toxicities on an ongoing basis. Once the principal investigator or coordinator becomes aware of an adverse event, the AE will be reported to the HRPO and QASMC according to institutional guidelines (please refer to Section 7.0).

Refer to the Washington University Quality Assurance and Data Safety Monitoring Committee Policies and Procedures for full details on the responsibilities of the DSMC at <https://siteman.wustl.edu/wp-content/uploads/2015/10/QASMC-Policies-and-Procedures-03.31.2015.pdf>

14.0 AUDITING

As coordinating center of this trial, Washington University (via the Quality Assurance and Safety Monitoring Committee (QASMC)) will monitor each participating site to ensure that all protocol requirements are being met; that applicable federal regulations are being followed; and that best practices for patient safety and data collection are being followed per protocol. Participating sites will be asked to send copies of all audit materials, including source documentation. The audit notification will be sent to the Washington University Research Patient Coordinator, who will obtain the audit materials from the participating institution.

Notification of an upcoming audit will be sent to the research team one month ahead of the audit. Once accrual numbers are confirmed, and approximately 30 days prior to the audit, a list of the cases selected for review (up to 10 for each site) will be sent to the research team. However, if during the audit the need arises to review cases not initially selected, the research team will be asked to provide the additional charts within two working days.

Items to be evaluated include:

- Subject screening and enrollment
- Reporting of adverse events
- Maintenance of HIPAA compliance
- Completeness of regulatory documentation
- Completeness of participant documentation
- Acquisition of informed consent
- IRB documentation
- Issues of protocol adherence

Additional details regarding the auditing policies and procedures can be found at <https://siteman.wustl.edu/wp-content/uploads/2015/10/QASMC-Policies-and-Procedures-03.31.2015.pdf>

15.0 STATISTICAL CONSIDERATIONS

This trial consists of an open-label phase I study, where the MTD and DLT of the combination of PD 0332991 will be determined, followed by a phase II study where patients with incurable HPV-unrelated SCCHN will be treated with PD 0332991 and cetuximab. The phase I portion of the study will adopt a 3 + 3 design and at most 12 patients will be needed in this group.

Dose escalations and de-escalations will proceed as follows after the occurrence of dose-limiting toxicity (DLT):

[figure not shown]
Cohort	# DLTs	Escalation Decision Rule
1	0	Escalate to dose 2.
	1	Enter 3 additional patients at dose 1.
	2	De-escalate to dose -1.
2	0	Conclude that the MTD has not yet been reached.
	1	Enter 3 additional patients at dose 2 if 0 in cohorts 1 and 2. Identify dose 2 as the MTD if 1 in cohorts 1 and 2.
	2	Conclude that dose 1 is the MTD.

For the phase II Arm 1 portion, based upon currently available data for cetuximab alone in platinum-resistant incurable SCCHN³⁷, an overall tumor response rate (CR + PR) of 13% or lower would be unacceptable and an overall tumor response rate of 26% or higher of clinical interest. A total of 30 eligible and evaluable patients will be accrued to the phase II portion of the study, and if 4 or more patients' tumors respond, the therapy will be accepted for further investigation. The design is based on Thall P and Sung H-G³⁸.

Assumes 13% response with standard treatment, response rate increase of 13% (26% response rate with experimental treatment), expected (grade 3 or 4) toxicity rate of 46% with standard, 0% allowable increase with experimental treatment.

Stop for poor response if:		Stop for excess (grade 3 or 4) toxicity if:	
# Patients is:	# Responses is ≤:	# cases of toxicity is ≥:	In 1 st # patients
3	0		
4	0	4	4
5	0	5	5
6	0	5	6
7	0	6	7
8	0	7	8
9	0	7	9
10	0	8	10
11	0	8	11
12	1	9	12
13	1	10	13

14	1	10	14
15	1	11	15
16	1	11	16
17	1	12	17
18	2	13	18
19	2	13	19
20	2	14	20
21	2	14	21
22	2	15	22
23	2	15	23
24	3	16	24
25	3	17	25
26	3	17	26
27	3	18	27
28	3	18	28
29	3	19	29
30	3	19	30

For the phase II arm 2 portion, the tumor response rate to any agent in patients with cetuximab-resistant incurable SCCHN is unknown but it is expected to be < 13%. An overall tumor response

rate (CR+PR) of 13% or lower would be unacceptable and an overall tumor response rate of 26% or higher would be of clinical interest. A total of 30 eligible and evaluable patients will be accrued to the phase II arm 2 portion of the study, and if 4 or more patients' tumors respond, the therapy will be accepted for further investigation. The design is based on Thall P and Sung H-G³⁸. The table and figure above also apply to phase II Arm 2.

For phase II Arm 3 portion, an overall tumor response rate (CR + PR) of 5% or lower would be unacceptable and an overall tumor response rate of 20% or higher of clinical interest. A total of 24 eligible and evaluable patients will be accrued to this arm. One or more tumor responses in the first 18 patients are required to continue enrollment. Two or more tumor responses in the first 24 patients are required to accept the alternative hypothesis. The design has probability = .74 of early stopping after the first cohort of 18 patients if the true response rate is 5% or less. The cumulative probability of completing the study (enrolling 24 patients) is 0.70 if the true response rate is 20% or greater. The design is based on Thall P and Sung H-G³⁸.

Number of patients	Cumulative probability of early stopping if response rate = 5% (null hypothesis)	Cumulative probability of early stopping if response rate = 20% (minimum alternative hypothesis)	Cumulative probability of continuing to end of study if response rate = 20% (minimum alternative hypothesis)
1	0	0	0
18	0.7436	0.2858	.7142
24	0.8335	0.2953	.7047

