5.2 Agent Administration

PD 0332991 should be taken by mouth on Days 1 through 21 of each 28-day cycle. **Patients should take PD 0332991 capsules with food.** Patients will be required to keep

a drug diary (Appendix B).

If a patient misses a day's dose entirely, s/he must be instructed not to make it up the next day but to just take his/her regular dose the following day. If a patient vomits any time after taking a dose, s/he must be instructed not to make it up but to resume subsequent dosing the next day as prescribed. If a patient inadvertently takes an extra dose during a day, s/he must be instructed to not take the next day's dose.

Cetuximab will be administered intravenously on a weekly schedule. The first dose of cetuximab will be 400 mg/m²; every week thereafter, patients will receive a dose of 250 mg/m². Patients will continue to receive weekly cetuximab at 250 mg/m² for the duration of their participation on study.

Upon IRB/EC approval of Amendment 5, a PD 0332991 oral solution will be available for patients who cannot swallow the PD 332991 capsules. Patients who begin the study receiving the oral solution will remain on the oral solution for the duration of their time on treatment in the study. Patients, who begin the study receiving capsules but develop difficulty swallowing the capsules and did not have disease progression, will be allowed to switch to the PD 0332991 oral solution. These patients will then remain on the oral solution for the duration of their time on treatment in the study. Each clinical site will be provided the oral solution Investigational Product Manual (IPM) containing the dosage and administration instructions (DAI) for preparation of the PD 0332991 oral solution. **Patients can take PD 0332991 oral solution with or without food.**

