5.6 Dosing for Phase II

Dosing for phase II will be administered as per Section 5.2. Dose of PD 0332991 will be 125 mg, which was the highest dose given in phase I (no MTD found). Thirty patients will

be enrolled to Arm 1 of phase II, 30 patients will be enrolled to Arm 2 of phase II, and 24 patients will be enrolled to Arm 3 of phase II. Enrollment for all arms may take place concurrently.

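### Arm 3 gets the same regimen as Arms 1 and 2 but has no pre-specified toxicity stopping rule; its only written stopping rule is for response

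*Combined protocol and SAP*

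**What the plan says.** **Regimen.** Section 5.6 sets one PD 0332991 dose for the whole of phase II: 125 mg, the top level tested in phase I, where no MTD was reached. Section 5.2 gives one cetuximab schedule with no arm-specific variant: "Cetuximab will be administered intravenously on a weekly schedule". Section 5.6 adds: "Enrollment for all arms may take place concurrently".

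**Arms 1 and 2.** The Arm 1 table in Section 15.0 has a response half and a toxicity half, the latter headed "Stop for excess (grade 3 or 4) toxicity if". Its stated basis is "expected (grade 3 or 4) toxicity rate of 46% with standard, 0% allowable increase with experimental treatment". The boundary starts at 4 toxicities in 4 patients and runs through 16 in 24 to 19 in 30. The Arm 2 paragraph ends: "The table and figure above also apply to phase II Arm 2".

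**Arm 3.** The next paragraph sets the size ("A total of 24 eligible and evaluable patients will be accrued to this arm") and the interim rule ("One or more tumor responses in the first 18 patients are required to continue enrollment"), and requires two or more responses in 24 to accept the alternative. It gives no toxicity rate, limit or look. It cites the same design reference as the other arms, whose title in the reference list concerns the monitoring of multiple outcomes.

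**Other oversight.** Section 13.0 provides for a DSMC toxicity review at least every 6 months once a secondary site is active, and for continuing monitoring by the investigator and coordinator. It refers to a DSMC charter for further duties. Section 5.9 allows the cancer center to close the study.

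**The concern.** The sponsor judged that this regimen needs a numerical toxicity boundary in two of three arms, and neither Section 1.8 (the Arm 3 rationale) nor Section 15.0 says why the third does without one. The omission looks like a by-product of adding Arm 3 in Amendment 6.

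Because the arms may enrol side by side, Arm 1 or Arm 2 could close on its toxicity boundary while Arm 3 continues on the same drugs, and no text links the decisions. Section 13.0 also asks the semi-annual report to list early stopping rules with supporting data; for toxicity in Arm 3 there is no rule to report against. At stake is how many Arm 3 patients are treated before a high toxicity rate forces a decision.

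**Working it through.** **Inputs (all from Section 15.0).** Toxicity boundary b(n) for n = 4 to 24: 4, 5, 5, 6, 7, 7, 8, 8, 9, 10, 10, 11, 11, 12, 13, 13, 14, 14, 15, 15, 16. For n = 25 to 30: 17, 17, 18, 18, 19, 19. Arm 3 response rule: at least 1 response in 18, then at least 2 in 24.

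**1. Is the printed boundary coherent?** The plan gives neither the priors nor the cutoff, so both are assumed. The rule tested stops when the posterior probability that toxicity is higher on the experimental than on the standard treatment reaches a cutoff. With a standard prior Beta(23, 27), an experimental prior Beta(1.38, 1.62) and a cutoff of 0.92, all 27 entries reproduce, and so does the blank at n = 3. Other settings also match all 27 entries, so the plan's exact inputs cannot be recovered. The calculations below need only the printed boundary.

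**2. Stop probability if the boundary covered Arm 3.** Let f(n, k) be the probability of k toxicities in n patients with no earlier stop, and p the true grade 3-4 rate:

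f(n, k) = f(n−1, k)(1−p) + f(n−1, k−1)p,

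where any mass at k ≥ b(n) is moved to stopped. Hand check at p = 0.60:
- By n = 4: 0.60^4 = 0.1296.
- At n = 5 nothing is added, since 5 of 5 would already have stopped at 4 of 4.
- At n = 6, exactly 3 of the first 4 and then both of the next 2: 4 × 0.60^3 × 0.40 × 0.60^2 = 0.1244.
- Cumulative by n = 6: 0.254.

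Full results, toxicity rule alone:

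| True grade 3-4 rate | Stop by 24 | Mean patients treated (of 24) | Stop by 30 (Arms 1 and 2) | Arm 3 as written |
|---|---|---|---|---|
| 46% | 0.163 | 21.6 | 0.173 | 0 |
| 50% | 0.247 | 20.4 | 0.269 | 0 |
| 60% | 0.549 | 16.4 | 0.612 | 0 |
| 70% | 0.851 | 11.5 | 0.908 | 0 |
| 80% | 0.984 | 7.4 | 0.995 | 0 |

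Every stop by 24 has occurred by patient 23: reaching 16 in 24 implies at least 15 in 23, which is already on the boundary.

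**3. What governs Arm 3 enrolment as written.** Only response does. P(all 24 enrolled) = 1 − (1 − r)^18, where r is the true response rate:
- r = 5%: 1 − 0.397 = 0.603
- r = 20%: 1 − 0.018 = 0.982

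These do not depend on toxicity.

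**4. Cost to the efficacy conclusion.** P(accept) = P(at least 2 of 24) − (1 − r)^18 × P(at least 2 of the last 6). At r = 20% this is 0.9669 − 0.0180 × 0.3446 = 0.961. Assuming toxicity and response are independent, multiply by P(no toxicity stop):
- 46% toxicity: 0.961 × (1 − 0.163) = 0.804
- 50% toxicity: 0.961 × (1 − 0.247) = 0.72

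Steps 3 and 4 use the response rule as written. The stopping probabilities printed for Arm 3 (0.7436 at 5%, 0.2858 at 20%) do not follow from that rule, which gives 0.397 and 0.018. That is a separate matter, and the toxicity gap does not depend on it.

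**The case against.** **Other safeguards exist.** A reader might infer that Arm 3 has no safety oversight beyond the six-monthly DSMC review. The documents do not support that. Section 13.0 has the investigator and coordinator monitoring continuously, Section 5.9 allows closure by the cancer center, Section 7 requires expedited reporting, and Section 6.1 sets individual dose modification. The DSMC can also see same-regimen toxicity from the other arms. All of this stands, but none of it carries a stated arm-level threshold, and it covers Arms 1 and 2 as well, where the sponsor still added a boundary. A limit in the DSMC charter cannot be excluded.

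**Antiretroviral eligibility.** A reader might infer that Arm 3 needs the rule more because it admits patients on antiretroviral therapy, whom Arm 1 excludes. Section 3.2 admits them to Arm 2 on the same terms, and Arm 2 has the boundary. The point does not set Arm 3 apart.

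**The 46% reference belongs to Arm 1.** It sits among the Arm 1 design assumptions, alongside data on cetuximab alone in platinum-resistant disease. Arm 3 is cetuximab-resistant and HPV-related, and no document gives a toxicity rate for that population. Section 15.0 also does not say whether events must be treatment-related or in which cycles they count. This stands as a reason for the sponsor to confirm the reference. It is not a reason to have no rule, since the sponsor already applies 46% to Arm 2, which is also cetuximab-resistant.

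**The rule costs power.** A drop from 0.96 to 0.80 is material in a 24-patient arm and has to be disclosed. The false-stop rate behind it (0.163) is slightly below the 0.173 already accepted over 30 patients.

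**Conclusion.** The gap is real. Section 15.0 gives Arms 1 and 2 a numerical toxicity boundary and gives Arm 3, on the same drugs and dose, response rules only. Once at least 1 of the first 18 patients has responded, no observed toxicity count stops Arm 3 under any rule in the documents. In Arms 1 and 2, 15 toxicities in 23 patients (65%) would stop accrual.

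Two stronger readings go too far. One is that Arm 3 will enrol all 24 patients at any toxicity rate: the response look at 18 can still close it (probability 0.397 at a 5% response rate), and so can discretionary oversight. The other is that Arms 1 and 2 would certainly stop at a high true rate. A stop is certain only once the observed count reaches the boundary; at a true rate of 60% the boundary misses within 24 patients with probability 1 − 0.549 = 0.451.

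The stop probabilities rest on the printed boundary and independent patients with a constant toxicity rate. The 0.80 acceptance figure also assumes independence of toxicity and response. Use of the boundary in Arm 3 assumes that 46% is a suitable reference there, which the documents do not establish. This is a cheap improvement that the sponsor should make, not a flaw that invalidates the arm.

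**What to change.** Add a sentence to the Arm 3 paragraph of Section 15.0 stating that rows 4 to 24 of the existing toxicity columns also apply to Arm 3. The sponsor should confirm the 46% reference rate for this arm, or state and justify another and recompute the boundary from it. If the omission was deliberate, or a limit sits in the DSMC charter, Section 15.0 should say so.

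Print the joint operating characteristics with the Arm 3 table: the toxicity-stop probability by 24 patients over a range of true rates, and the chance of acceptance with both rules in force.

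The change needs no extra patients or procedures. Its price is a 0.16 chance of a false toxicity stop at a true rate of 46%, with acceptance at a 20% response rate falling from 0.96 to about 0.80 at 46% toxicity, and to about 0.72 at 50%, under independence.

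### Arm 3's stated stopping and completion probabilities do not follow from its written rule: 0.74 should be 0.40, 0.29 should be 0.02, and false acceptance is 0.33 against an implied 0.17

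*Combined protocol and SAP*

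**What the plan says.** Section 15.0 (Statistical Considerations) sets the Arm 3 null hypothesis: "For phase II Arm 3 portion, an overall tumor response rate (CR + PR) of 5% or lower would be unacceptable". The alternative is set in the same sentence: "an overall tumor response rate of 20% or higher of clinical interest". The sample size is fixed: "A total of 24 eligible and evaluable patients will be accrued to this arm".

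Two decision rules follow.

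- Interim: "One or more tumor responses in the first 18 patients are required to continue enrollment".
- Final: "Two or more tumor responses in the first 24 patients are required to accept the alternative hypothesis".

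The operating characteristics come next. "The design has probability = .74 of early stopping after the first cohort of 18 patients if the true response rate is 5" per cent or less. "The cumulative probability of completing the study (enrolling 24 patients) is 0.70 if the true response rate is 20% or greater". A short table gives cumulative early-stopping probabilities of 0.7436 (5%) and 0.2858 (20%) at 18 patients, and 0.8335 and 0.2953 at 24. Its last column gives the chance of continuing to the end at 20% as 0.7142 and 0.7047.

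The patient-by-patient response and toxicity boundaries printed for Arm 1 are extended to one other arm only: "The table and figure above also apply to phase II Arm 2". No toxicity stop, and no response look before patient 18, is written for Arm 3.

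**The concern.** With one interim look at a response count of zero, the stopping probability is a single power of the non-response rate, so the printed 0.74 can be checked directly. It is almost double the correct value. At 20% the printed value is about 16 times the correct one (0.2858 / 0.018).

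Objective response is Arm 3's primary objective (Section 2.1), and these are the only error rates given for it. Followed as written, the plan protects much less well against an inactive regimen than the table suggests. At 5%, the last six patients are enrolled with probability 1 − 0.397 = 0.603, not 1 − 0.7436 = 0.256, and the regimen is accepted about one time in three. If instead the table reflects the intended design, a stopping rule is missing from the protocol, and that rule would end a sizeable share of truly active arms early.

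**Working it through.** **Inputs**, all from the Arm 3 paragraph and table in Section 15.0: p0 = 0.05, p1 = 0.20; stop if 0 of 18 respond; accept if at least 2 of 24 respond.

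**Step 1. Stop at 18.** P(stop) = (1 − p)^18.

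- 5%: 0.95^18 = 0.3972
- 20%: 0.80^18 = 0.0180

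**Step 2. Not accepted by 24.** This happens if the arm stops at 18, or has exactly 1 response in 18 and none in the next 6:

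P(not accepted) = (1 − p)^18 + 18p(1 − p)^17 × (1 − p)^6

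- 5%: 0.3972 + 0.3763 × 0.7351 = 0.3972 + 0.2766 = 0.6738, so P(accept) = 0.3262
- 20%: 0.0180 + 0.0811 × 0.2621 = 0.0180 + 0.0213 = 0.0393, so P(accept) = 0.9607

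**Step 3. Enrol all 24 at 20%.** 1 − 0.0180 = 0.9820.

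| Quantity | Written rule | Plan |
|---|---|---|
| Stop at 18, 5% | 0.397 | 0.7436 |
| Stop at 18, 20% | 0.018 | 0.2858 |
| Not accepted by 24, 5% | 0.674 | 0.8335 |
| Not accepted by 24, 20% | 0.039 | 0.2953 |
| Enrol all 24, 20% | 0.982 | 0.70 |
| Accept, 5% | 0.326 | 0.167 (implied, 1 − 0.8335) |
| Accept, 20% | 0.961 | 0.705 (implied, 1 − 0.2953) |

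**Step 4. Can a simple slip explain the printed figures?**

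- Rounding: no. 0.7436 would need a true response rate of 1 − 0.7436^(1/18) = 1.6%, and 0.2858 one of 6.7%.
- Mistyped interim cut-off: no. Stopping at 1 or fewer of 18 gives 0.774 and 0.099; 2 or fewer gives 0.942 and 0.271. Neither matches both columns.
- Arm 1/2 response boundaries used for Arm 3: no. They give 0.976 and 0.597 by patient 18.
- Written rule plus a stop independent of response (toxicity, say): no. Such a stop would multiply the chance of continuing past 18 by the same factor at both rates. The factors needed are 0.2564 / 0.6028 = 0.43 at 5% and 0.7142 / 0.9820 = 0.73 at 20%.

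**Step 5. Where the figures may come from (inference only).** Adding a stop for 0 responses in the first 6 patients gives 0.95^6 = 0.735 and 0.80^6 = 0.262 by 18, and 0.827 and 0.269 by 24. Dividing the plan's continuation probabilities by this rule's gives:

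| Look | 5% | 20% |
|---|---|---|
| 18 | 0.2564 / 0.2649 = 0.968 | 0.7142 / 0.7379 = 0.968 |
| 24 | 0.1665 / 0.1727 = 0.964 | 0.7047 / 0.7308 = 0.964 |

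The factor is the same at both response rates. That is the pattern expected from a look at 6 patients plus a second stop, unrelated to response, of about 3.2% by 18 and 3.6% by 24.

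**The case against.** The arithmetic for the written rule is not open to dispute, but four points can be made for the plan.

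1. *The documents show a conflict, not which side of it is wrong.* This stands. The values 0.40 and 0.02 are correct for the rule as written. If the rule was mis-stated, the repair belongs in the rule. The fix allows for both.

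2. *No false-acceptance rate or power is stated for Arm 3.* Also true. The 0.167 and 0.705 come from reading the 24-patient row as final non-acceptance, although the column is headed as early stopping and the text describes 0.70 as the chance of enrolling 24. The comparison with 0.33 and 0.96 rests on that reading. The 0.33 and 0.96 themselves do not, and neither does the mismatch at 18 patients.

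3. *The cited method is Bayesian and monitors more than one outcome, so a toxicity component may be included.* A Bayesian method may generate the boundaries. Once they are stated as response counts, their probabilities at fixed rates of 5% and 20% are binomial. A toxicity stop cannot rescue the written rule (step 4). The 6-patient reconstruction also remains conjecture: no section mentions such a look, and no documented parameter yields the residual stop of 3% to 4%. The Arm 1/2 toxicity boundaries at their stated 46% rate would stop 14.6% of arms by 18 and 16.3% by 24, which is much more.

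4. *The decision rule is explicit and can be followed, and an observed response rate with its interval can still be read.* That is fair. What fails is the stated justification of the design and the error rates attached to an accept or reject decision.

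**Conclusion.** The point holds and must be corrected. For the rule as written, all four tabulated stopping probabilities and the 0.70 completion probability are wrong. The errors are 0.35 (5%) and 0.27 (20%) for stopping at 18, and 0.16 and 0.26 for non-acceptance by 24. A regimen at the unacceptable 5% rate is accepted with probability 0.33, and one at 20% with probability 0.96.

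This assumes independent binary responses, exactly the two looks described, and 24 evaluable patients. The implied 0.17 and 0.705 further assume that the 24-patient row means non-acceptance. If the table came from a design with a look at 6 patients, that look alone would stop 0.80^6 = 26% of arms with a true rate of 20%. That consequence is conditional on a rule the documents do not contain.

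**What to change.** Make the rule and the figures agree, in one of two ways.

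- **If the written rule stands**, replace the two probability sentences and the table with: probability of stopping at 18 of 0.40 (5%) and 0.02 (20%); probability of enrolling all 24 at 20% of 0.98; false-acceptance probability 0.33; power 0.96. Label the 24-patient row as non-acceptance (0.67 and 0.04), so that it is not read as early stopping.
- **If an earlier look or a second stopping criterion was intended**, write it into the Arm 3 rule in full and recompute every figure from it.

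Either way the cost is amendment wording and a recomputed table, with no extra patients.

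As a separate and optional design choice, a false-acceptance rate of 0.33 may be judged too high. Two responses in 24 (8.3%) has an exact 95% confidence interval of 1.0% to 27.0%, which includes both 5% and 20%. Keeping 24 patients and the 18-patient look, but requiring at least 3 responses to accept, gives false acceptance 0.115 and power 0.884. That lowers power from 0.96 to 0.88, still above the implied 0.705. The plan sets no error-rate target for Arm 3 that would require this change.
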